## **6. ANALYSIS SETS**

### **6.1 INTENTION-TO-TREAT**

The intent-to-treat population will consist of all subjects who are randomized and receive the actual study treatment (GS010). This population will be the population for the primary efficacy analysis.

## 6.2 PER-PROTOCOL POPULATION

The per-protocol population (PP) will consist of all subjects who are randomized, receive the actual study treatment (GS010 and sham treatment) and complete the Week 48 ETDRS assessment without any major protocol deviation. This population will be the population for the supportive analysis of primary efficacy analysis.

## 6.3 SAFETY

The safety population is defined as those subjects who received study treatment (GS010). This population will be used as the population for all safety analyses.

## 7. INTERIM ANALYSES

An interim analysis is not planned for this study.

### 7.1 TIMING OF PRIMARY ANALYSIS

Primary endpoint analysis will be performed as soon as the last subject completes the Week 48 assessment and data are cleaned. At that point, all subjects will be recruited and followed for at least 48 weeks except in case of premature withdrawal. Many subjects will have reached Week 96 but not all of them. The study will be formally unmasked for the efficacy analysis at Week 48. The study will still continue up to scheduled end (Week 96). Although the study will have been unmasked for the study statistician, every effort (see Appendix V in Section 20.5 of the V3.0 protocol) will be invested to maintain the masking of subjects and personnel in charge of the conduct of the study including study managers, data managers, CRAs, investigators (except international coordinating investigators per Appendix V in Section 20.5 of the V3.0 of the protocol).

**Data Safety Monitoring Board (DSMB):** An independent DSMB will be constituted and responsible for periodically reviewing study data to assure the continued safe conduct of the study. The DSMB will meet to review the data at least every 6 months. Operational and logistical details will be provided in a separate DSMB charter.

## 8. DATA REVIEW

### 8.1 DATA HANDLING AND TRANSFER

Details regarding the data handling and data transfer process can be found in the PRA Clinical Informatics Plan.

## 8.2 DATA SCREENING

Beyond the data screening built into the PRA Data Quality Plan, the PRA programming of analysis datasets, tables, figures, and listings (TFL) provides additional data screening. Presumed data issues will be output into SAS logs identified by the word “Problem”, “ERROR,” “WARNING,” and “uninitialized,” and extracted from the logs by a SAS macro and sent to Data Management.

Review of a pre-freeze TFL run on clean subjects and a post-freeze TFL run on the frozen database allow for further data screening prior to lock. The post-freeze TFL at Week 48 will be discussed with GenSight in a masked data review meeting to identify any final data issues and seek corrections prior to data-base lock. The PRA statistician and GenSight must approve database lock. The same procedure will be performed before the W96 database lock.

## 9. STATISTICAL METHODS

All analyses will use SAS version 9.4 or higher.

Unless otherwise noted, categorical variables will be summarized using counts and percentages. Percentages will be rounded to one decimal place, except 100% and 0% which will be displayed without any decimal places.

Continuous variables will be summarized using the number of observations (n), mean, standard deviation (SD), median, first quartile (Q1), third quartile (Q3), minimum and maximum. Minimum and maximum will be rounded to the precision of the original value.

Rounding rules are generally as follows:

- If the original value has 0 decimal places: mean, median, SD, Q1, Q3 and 95% confidence intervals (CIs) have 1 decimal place.
- If the original value has 1 decimal place: mean, median, SD, Q1, Q3 and CIs have 1 decimal place.
- If the original value has 2 or more decimal places: mean, median, Q1, Q3, CIs, and SD have the same decimal places as the original measure, up to a maximum of 3 decimal places.
- P-values will be presented as four decimal places.

Summary TFLs will be in landscape orientation and display standard headers containing the sponsor name (“GenSight Biologics”) as well as a standard footer containing the name of the program used to generate the display, its path, and a date/time stamp. Headers, footers, titles, and column headers for tables will be repeated on every page of each display; pages will be numbered “Page x of y.” Visit labels in tables and figures will show visit name. Summary TFLs containing no applicable data will display a line reading, “No applicable data were reported” or similar language. Dates and times will be presented using the DDMONYYYY HH:MM format. Summary TFLs will be produced using SAS® Output Delivery System (ODS) to generate rich

text format (RTF) files and/or PDF files, if necessary. The default font will be 9-point Times New Roman, and minimum margins will be top 1", bottom 1", left 1", right 1" (US letter). Standard indentation for subheadings is 2 spaces, and standard footnote indicators will be lowercase letters (e.g., a, b, c). Individual files will be named with the table, figure, or listing number plus the program name (with more descriptions related to output), concatenated with underscores and using leading zeros as necessary for alphabetical sorting (e.g., T\_14\_1\_1\_disp). Listings will be sorted by location (Right/left), treatment and subject number if appropriate. For the listings where location and treatment are not appropriate, listings will be sorted by subject number only.

## **9.1 SUBJECT DISPOSITION**

The number and percentage of subjects, who were screened, randomized, treated in the study, who completed the study, and the number of subjects who completed the Week 48, Week 72 and Week 96 visits will be presented, together with the number and percentage of subjects who withdrew from the study prematurely and a breakdown of the corresponding reasons for withdrawal. The withdrawal data will be presented overall, as well as presenting withdrawal before Week 48 and withdrawal after Week 48. This data will also be listed according to the eCRF. The number and percentage of subjects in ITT, PP and safety population will also be presented.

Number of subjects who missed visits among all the subjects will be presented. In addition, number of missing data for visual acuity and important SD-OCT parameters will also be summarized.

## **9.2 PROTOCOL DEVIATIONS AND VIOLATIONS**

All major protocol deviations will be identified. A sensitivity analysis of the primary end point will be performed based on per-protocol analysis population. All the major protocol deviations will be listed. The decision regarding the major protocol deviations will be taken during the masked data review meeting. All the major protocol deviations will be identified and recorded in the Clinical Trial Management System (CTMS) of PRA.

## **9.3 DEMOGRAPHIC AND BASELINE CHARACTERISTICS**

Demographic and baseline characteristics (gender, age, weight, height) will be summarized using descriptive statistics. Qualitative variables (gender) will be summarized using frequencies while quantitative variables (age, weight, height) will be summarized using mean, SD, median, Q1, Q3, minimum and maximum.

Demographic and baseline characteristics will be summarized for the ITT and Safety Population. The analysis will be presented in two ways: Best-GS010 vs Best-Sham and Worst-GS010 vs Worst-Sham.

Demographic and Baseline Characteristics will also be summarized as: Best-GS010 vs Best-Sham and Worst-GS010 vs Worst-Sham for on chart eyes at baseline.

This data will also be listed based on the data listed in the eCRF.

Medical history data will be summarized by using counts and percentages and will be presented by system organ class and preferred term. Duration of vision loss at the Screening will be summarized by treatment group (All-GS010 vs All Sham, Best-GS010 vs Best-Sham and Worst-GS010 vs Worst-Sham). For the All-GS010 versus All-Sham comparison the safety population will be used for analysis, whereas for the Best-GS010 versus Best-Sham comparison and the Worst-GS010 versus Worst-Sham comparison the ITT population will be used for analysis of the duration of vision loss.

Duration of vision loss will also be presented between All-GS010 and All-Sham for on chart eyes and off-chart eyes at baseline.

## **9.4 TREATMENTS**

### **9.4.1 Extent of Study Drug Exposure**

This study includes a single IVT injection in randomized eye and a single sham IVT injection in fellow eye on same day. Therefore, no summary table will be produced for the exposure data. eCRF data related to IMP administration will be listed.

### **9.4.2 Concomitant Treatments**

Prior and concomitant treatments will be coded using the World Health Organization dictionary (WHO Drug Dictionary Version 01Mar2015 DDE, B2). For each medical entity all Anatomical Therapeutic-Chemical (ATC) codes will be assigned according the therapeutic classes to which the treatment belongs. Coding of Treatments is detailed in the Coding Guidelines.

Prior and concomitant treatments will be summarized for the Safety population by number and percentage of subjects of WHO Drug Dictionary ATC levels (ATC1, ATC2) and preferred term. All prior and concomitant treatment data will be listed.

## **9.5 EFFICACY ANALYSES**

All efficacy analysis will be conducted on the ITT population and analyzed by actual treatment received. Sensitivity analysis will be performed based on a PP Population.

### 9.5.1 Primary Variable

Primary variable will be analyzed by using two approaches:

For EMA, the change of LogMAR from baseline to Week 48 will be analyzed between all-GS010 treated eyes and all-Sham treated eyes.

The FDA has recommended comparing GS010 vs Sham in the Best-seeing eyes as a primary analysis. Therefore, for the FDA change of LogMAR from baseline to Week 48 will be analyzed between Best-GS010 treated eyes and Best-Sham treated eyes as the primary analysis.

The approach to analyze the primary variable is different for EMA and FDA. For EMA the analysis is based on intra-subject comparison of change of LogMAR from baseline to Week 48. For FDA, the analysis is based on inter-subject comparison of change of LogMAR from baseline.

The two approaches are stated below in detail:

#### Primary Analysis for EMA

The null and alternative hypotheses for the primary endpoint are defined below

$$H_0: \mu_{\text{All-GS010}} = \mu_{\text{All-Sham}}$$

$$H_1: \mu_{\text{All-GS010}} \neq \mu_{\text{All-Sham}}$$

Where  $\mu$  presents the mean change from baseline to Week 48 in LogMAR. “All” represents all eyes treated with GS010 or Sham

The primary analysis will be performed on the ITT population. The change from baseline to Week 48 in the LogMAR acuity will be the primary response. The change from baseline of all-GS010 eyes will be compared to the change from baseline of all-Sham eyes (intra-subject comparison) using a mixed model of analysis of covariance (ANCOVA) using the following terms (or covariate) in the model:

- Subject as random factor
- Eyes of the subject as random factor,
- Treatment and the
- Baseline LogMAR for each eye.

The analysis will be performed based on alpha of 0.05. The statistical significance in favor of GS010 against sham will provide evidence of the advantage of using GS010 for halting visual acuity loss or improving visual acuity in subjects with LHON with duration of vision loss of 6 months or less. The difference in the mean change from baseline (adjusted mean difference) to Week 48 between the two treatment groups and associated 95% confidence interval will be reported.

The center will not be included in the analysis as the number of subjects recruited per site will be very small. However, stratification by geographical area will be performed as a sensitivity analysis. Neighboring countries can be pooled together to reach at least 9 subjects per geographical entity. The pooling will be performed during the masked review of data.

All the model diagnostics will be checked.

#### Secondary analysis of primary variable for EMA

Secondary Analysis of primary variable for EMA will be based on the methods for the primary analysis of the primary variable for FDA stated below, using ANCOVA. For secondary analysis, change of LogMAR from baseline at Week 48 will be compared between best-seeing GS010 eyes and best-seeing Sham eyes (inter-subject comparison). In addition, a secondary analysis of change in LogMAR from baseline between worst-seeing eye treated with GS010 or Sham will be performed.

#### Other Analysis

Summary statistics for LogMAR and ETDRS score and change from baseline will be presented by treatment group (All-GS010/All-Sham).

Summary statistics for LogMAR and change from baseline will be presented by treatment group for on chart eyes at baseline (All-GS010/All-Sham).

Summary statistics for LogMAR and change from Nadir and time to Nadir will be presented by treatment group (All-GS010/All-Sham).

A graph presenting the mean of each treatment group at baseline and the mean at all the timepoints (Week 48,72 and 96)Week will be presented. The graph will be useful to assess whether the difference in the change from baseline is mainly due to the difference at baseline or the difference at Week 48.

#### Sensitivity Analyses

The primary analysis with the same model will be repeated for the following lists.

- 1) Per protocol
- 2) Randomized subjects even if they were not treated and assigned treatment by randomization instead of actual treatment received
- 3) Secondary handling of missing data
- 4) Model with geographical area effect
- 5) Model excluding major outliers if any
- 6) Analysis of absolute Week 48 LogMAR values
- 7) Baseline GCL thickness/volume
- 8) Best or worst-seeing eye (eye status) added as a binary covariate
- 9) Duration of vision loss at the time of Screening added as a covariate in the model

All these analyses will be presented in a forest plot displaying treatment effect, 95% confidence intervals and p-value. The analysis will also be presented in tabular format.

- 10) Non-parametric Analysis: Wilcoxon signed-rank test will be performed as a sensitivity analysis to compare between all-GS010 eyes and all-Sham eyes
- 11) On-chart eyes at baseline
- 12) Off-chart eyes at baseline
- 13) Analysis of absolute Week 48 LogMAR values for on-chart eyes at baseline
- 14) On-chart eyes at baseline and per protocol population
- 15) On-chart eyes at baseline and all randomized subjects
- 16) On-chart eyes at baseline and Secondary handling of missing data
- 17) On-chart eyes at baseline and Duration of vision loss at the time of Screening added as a covariate in the model
- 18) On-Chart eyes at baseline and at Week48, Week 72 and Week 96
- 19) Off-Chart eyes at baseline and at Week48, Week 72 and Week 96

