4 STUDY PLAN

4.1 Study Design

GS-LHON-CLIN-03A is a Phase III double-masked, sham-controlled, multicenter, multicountry, study. Recruitment is competitive.

Both eyes will receive standard antiseptic preparation, administration of topical local ocular anesthetic agents and will undergo pupillary dilation. Administration of an IOP lowering agent will precede treatment. GS010 will be administered once during the study via a single IVT injection. Sham IVT injection will be performed whereby pressure will be applied to the eye at the site of a typical procedure using the blunt end of a syringe without a needle.

The right eye of each subject will be randomly allocated to receive either GS010 or sham treatment in a 1:1 allocation ratio. The fellow (left) eye will receive the treatment not allocated to the right eye. Therefore, each subject will receive GS010 in one eye and sham treatment in the fellow eye.

An algorithm with a testing hierarchy will be employed to determine the better- and worse-seeing eye of each subject prior to randomization. The randomization will be based on the right and left eye, because if the right eye is treated the left eye will receive sham and vice versa the treatment groups will be automatically balanced. However, the better- or worse-seeing eye at entry can be a confounding factor, and it cannot be discarded that the treatment effect will be the same in the better and worse seeing-eye. Secondarily, in order to verify this hypothesis, an adaptive randomization technique called Efron's minimization method will be used to minimize the imbalance of treatment groups between the better-seeing eyes treated and worse-seeing eyes treated.

Masking will be accomplished with sham injection of the fellow eye. Thus, treatment allocation will be double-masked for both the subject and the investigation (follow-up) team. The pharmacy team, as well as the physician and medical team performing the GS010 administration and sham injection will be unmasked to treatment allocation. This treating, unmasked medical team will also perform the first follow-up visit (Visit 4), as well as focused follow up of ocular adverse events commencing at Visits 3 and 4 until

resolution of the AE or the determination that no further clinical evolution is expected. Centralized analysis of ETDRS, automated visual fields, SD-OCT, color vision and contrast sensitivity will be performed.

Trial visits:

The trial is divided into the following visits:

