8.6 Method of Assigning Treatment

The right eye of each subject will be randomly allocated to receive either GS010 or sham treatment in a 1:1 allocation ratio. The fellow (left) eye will receive the treatment not allocated to the right eye. Therefore, each subject will receive GS010 in one eye and sham treatment in the fellow eye. Prior to randomization, each subject's better- and worse-seeing eye will be determined. Efron's minimization method will be used in the randomization process to balance as much as possible the two treatment groups (GS010 and sham) in the better-seeing eyes.

To enroll a subject (Visit 1), the Investigator will call an interactive response system (IRS) and provide brief details about the subject to be enrolled. Each subject will receive a subject number assigned at screening, which will serve as the subject identifier throughout the study. The subject number will be required in all communication between the Investigator (or designee) and the IRS regarding a particular subject. Subject numbers will be tracked via the IRS.

To randomize a subject (Visit 2), the masked Investigator (or designee) will call the IRS and provide brief details about the subject to be randomized. Eligible subjects will be randomized in a 1:1 ratio (right/left eye), taking into account the Efron's minimization method, using the IRS.

The IRS User Guide will describe the steps of the randomization process from the subject's screening up to before IVT injection.

An algorithm with a testing hierarchy will be employed prior to randomization to determine the better- and worse-seeing eye of each subject, as follows:

- 1. ETDRS visual acuity score for subjects able to read the ETDRS chart. The eye with the higher ETDRS score is the better-seeing eye. For subjects who cannot read the ETDRS chart ("off chart" subjects) a standard study procedure will be used to determine visual acuity based on counting fingers at a given distance. The eye with the best visual acuity based on this method is the better-seeing eye. If one eye of a subject is able to read letters on the ETDRS chart and one eye cannot, the eye able to read the ETDRS chart is the better-seeing eye.
- 2. SD-OCT parameters (to be used if there is no inter-eye difference based on Criterion 1):

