12.2 Sample Size

Sample size calculation is based on the primary endpoint (LogMAR) and on the paired comparison of treated and sham eye. There is no published data regarding the within subject variance and the sample size calculation through paired comparison will therefore be very speculative for two reasons. The first reason is the within subject correlation between right and left eye and the second reason is the absence of information on the within and between subject variance of the LogMAR. Usually the within subject correlation is positive and the use of a null correlation is conservative. The absence of information on the LogMAR requires a second rough approximation of the mean and variance of LogMAR because the mean of ETDRS (Lam et al. 2014) is highly correlated to the variance of ETDRS ($R^2 = 0.839$ for the log-log relationship). This correlation is in favor of the use of the LogMAR to stabilize the variance but the transformation from ETDRS mean and variance to LogMAR mean and variance requires additional assumptions. Starting with a mean 23.4 and a standard deviation of 28.3 (Lam et al. 2014) and a difference of 20 letters on average between treated and sham eye, using the relationship between the log mean and the log variance obtained with Lam et al. (2014) results (log variance = 1.743 log mean + 0.48, $R^2 = 0.839$) and assuming a perfect lognormal distribution of ETDRS, the difference in means of the lognormal distributions is 0.65 (3.32 - 2.67) and the pooled standard deviation of the log distributions is 0.914. Assuming no correlation between both eyes, the within subject standard deviation is $(2x0.914^2)^{0.5} = 1.29$. The standardized difference in means is therefore 0.65/1.29 = 0.504 rounded to 0.50. The sample size required to get a power of 85% is exactly 36 subjects.

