## 3.3 SAMPLE SIZE CONSIDERATIONS

Sample size calculation is based on the primary endpoint (LogMAR) and on the paired comparison of treated and sham eye. There is no published data regarding the within subject variance and the sample size calculation through paired comparison will therefore be very speculative for two reasons. The first reason is the within subject correlation between right and left eye and the second reason is the absence of information on the within and between subject variance of the LogMAR. Usually the within subject correlation is positive and the use of a null correlation is conservative. The absence of information on the LogMAR requires a second rough

approximation of the mean and variance of LogMAR because the mean of ETDRS (Lam et al. 2014) is highly correlated to the variance of ETDRS ( $R^2 = 0.839$  for the log-log relationship). This correlation is in favor of the use of the LogMAR to stabilize the variance but the transformation from ETDRS mean and variance to LogMAR mean and variance requires additional assumptions. Starting with a mean 23.4 and a standard deviation of 28.3 (Lam et al. 2014) and a difference of 20 letters on average between treated and sham eye, using the relationship between the log mean and the log variance obtained with Lam et al. (2014) results (log variance =  $1.743 \log \text{mean} + 0.48$ ,  $R^2 = 0.839$ ) and assuming a perfect lognormal distribution of ETDRS, the difference in means of the lognormal distributions is 0.65 (3.32 - 2.67) and the pooled standard deviation of the log distributions is 0.914. Assuming no correlation between both eyes, the within subject standard deviation is  $(2 \times 0.914^2)^{0.5} = 1.29$ . The standardized difference in means is therefore  $0.65/1.29 = 0.504$  rounded to 0.50. The sample size required to get a power of 85% is exactly 36 subjects.

In GS-LHON-CLIN-01(Phase I/II study), at Week 48 the standard deviation (SD) for visual acuity of the between-eye difference in change from baseline was calculated as 0.594. Considering that in Phase III studies of GS010 detection of a 15 ETDRS letters or 0.3 LogMAR difference between treated and untreated eyes at outcome is a clinically reliable difference, the SD of the difference of 0.594 would provide a power/probability of 84% to detect such a difference based on the enrolment goal of 36 subjects each in the RESCUE and REVERSE Phase III clinical trials.

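### Eye status, the factor the minimisation balances, is missing from the EMA primary model, so the primary interval may be wider than it needs to be if status predicts change beyond baseline LogMAR

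*SAP*

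**What the plan says.** **Allocation.** Each subject receives GS010 in one eye and sham in the other. Protocol 8.6 (repeated in SAP 3.4) says that Efron's "minimization method will be used in the randomization process to balance as much as possible the two treatment groups", here among the better-seeing eyes. Protocol 4.1 gives a reason: "the better- or worse-seeing eye at entry can be a confounding factor". SAP 4.3 also lists eye status among the potentially important prognostic factors.

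**Primary model.** The EMA primary analysis (SAP 9.5.1) is a mixed ANCOVA of change in LogMAR at Week 48. Subject and eye are random, treatment is fixed, and the only covariate is "Baseline LogMAR for each eye". Protocol 12.4.1 describes the same model in substance: subject, treatment and baseline.

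**Where status does appear.** It is item 8 of the EMA sensitivity analyses ("Best or worst-seeing eye (eye status) added as a binary covariate"). It is also a main effect and a treatment interaction in the time-course MMRM (SAP 9.5.5), defines the separate best-eye and worst-eye ANCOVAs, and forms part of the interaction model in protocol 12.4.1. No reason is given for including it in the MMRM but not in the primary model for the same response.

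The FDA primary analysis uses best-seeing eyes only, so status is constant there and this point does not apply.

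**The concern.** A factor that the allocation balances normally belongs in the analysis model. In this paired design, a status effect adds a positive shift to the GS010-minus-sham difference when the better eye is treated, and an equal negative shift when the worse eye is treated. Balanced allocation cancels these shifts in the mean. If they are not modelled, they remain in the residual variance, so the trial balances the factor without taking the precision that balance offers.

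An effect beyond baseline acuity is plausible from the documents. The protocol summary puts the median delay between first-eye and second-eye involvement at 2 months, and selection criterion 2 requires vision loss in only one eye. A subject's two eyes may therefore be at different disease stages. Onset is recorded per eye (SAP 5.6), but duration is also outside the primary model. When acuity ties, SAP 3.4 sets status by OCT, contrast sensitivity or investigator judgement, which baseline LogMAR does not carry.

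Sensitivity analysis 8 cannot stand in for the primary result. SAP 9.5.3 spends all of the alpha on the primary endpoint analysis, and protocol Appendix V bars SAP amendments once the code is broken.

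**Working it through.** **Inputs from the documents.** N = 36, SD of the between-eye difference in change 0.594, and target difference 0.3 LogMAR (SAP 3.3). "The analysis will be performed based on alpha of 0.05", with a two-sided alternative (SAP 9.5.1). Protocol 12.2: "The standardized difference in means is therefore 0.65/1.29 = 0.504 rounded to 0.50".

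**Assumptions not in the documents.** The residual status shift g (varied from 0 to 0.5 LogMAR); an exact 18/18 split of better-eye and worse-eye treated subjects; a half-normal between-eye baseline gap; and a baseline slope of -0.5. The SD of 0.594 is used as the residual SD, although the SAP does not say it is baseline-adjusted.

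**1. The plan's own figures.** n = ((1.960 + 1.036)/0.50)² = 35.9, so 36, which agrees with "The sample size required to get a power of 85% is exactly 36 subjects". For the second justification, 0.3/0.594 = 0.505, and noncentral-t power with 35 df is 83.8%, matching the stated 84%. The planning half-width is 2.030 × 0.594/√36 = 0.201 LogMAR.

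**2. How status enters.** For subject i, the paired difference is D = τ + βx + g·s + e. Here s = +1 if the better eye received GS010 and -1 otherwise, x is the between-eye baseline difference, and SD(e) = 0.594.

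**3. Baseline effect ignored (not the SAP's model).** The excess width without status is (t₃₄/t₃₃)·√(1 + g²/0.594²) - 1, with t₃₄ = 2.0322 and t₃₃ = 2.0345. At g = 0, 0.1, 0.2, 0.3 and 0.5 this gives -0.1%, +1.3%, +5.4%, +11.9% and +30.6%.

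**4. Baseline difference in both models.** Status is defined first by baseline acuity, so x and s are strongly correlated. With a half-normal gap the squared correlation is 2/π = 0.637, which leaves 1 - 0.637 = 0.363 of g² for a status term to remove. Adding status also costs one df and some collinearity with x: √[(1 + 0.363/36)/(1 + 1/36)] × 2.0322/2.0345 = 0.990. So the excess is about 0.990·√(1 + 0.363g²/0.594²) - 1. At g = 0.3 this is 0.990 × √1.0926 - 1 = +3.5%. Simulated mean half-widths (gap SD 0.4) agree:

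| g (LogMAR) | Without status | With status | Excess without |
|---|---|---|---|
| 0 | 0.2009 | 0.2031 | -1.1% |
| 0.1 | 0.2018 | 0.2030 | -0.6% |
| 0.2 | 0.2050 | 0.2030 | +1.0% |
| 0.3 | 0.2101 | 0.2032 | +3.4% |
| 0.5 | 0.2252 | 0.2027 | +11.1% |

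Gap SDs of 0.2 and 0.8 give essentially the same results. Break-even is where 0.363g²/0.594² = 1/0.990² - 1 = 0.0203, that is g ≈ 0.14 LogMAR, or 7 letters at 5 letters per 0.1.

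**5. Mixed-model fits.** With random subject, treatment and eye-level baseline (the SAP's form), the excess standard error without status was about 0 to +1% at g = 0, +1 to +4% at 0.1, +3 to +9% at 0.2, +7 to +17% at 0.3 and +21 to +37% at 0.5. A single baseline slope then serves both between and within subjects, so baseline is less free to stand in for status. These runs further assume a between-eye correlation of 0.5, slopes from -0.3 to -0.8, and gap SDs of 0.2 or 0.5.

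**6. Validity.** Across the paired simulations, coverage of the 95% interval without status was 0.949 to 0.960.

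**The case against.** The strongest reply is that baseline LogMAR already does most of this work, because it is in the model and is the first criterion for status. That is largely right. It is why the gains in step 4 are much smaller than those in step 3, and why nothing is gained when the residual shift is small.

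The plan also links the minimisation to a secondary question. Protocol 4.1 and 12.1 use it to examine whether the effect differs between better and worse eyes, and the paired design balances treatment by itself. The adjusted estimate will be reported in any case, with its interval and p-value, under item 8. These points limit the importance of the matter. They do not explain why the less adjusted of two prespecified models should be primary.

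Three stronger readings are tempting, and the documents support none of them:

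- A reader might infer that the interval is certainly too wide. That requires a status effect beyond baseline LogMAR, and the documents report none.
- A reader might subtract an assumed shift of 0.1, 0.2 or 0.3 from the variance 0.594² and read off power of 84.8%, 87.8% or 92.7% in place of 83.8%. Those figures leave baseline LogMAR out of both models, so they are not the gain for the SAP's model.
- A reader might infer bias or a faulty type I error rate. With near-balanced allocation the estimate is unbiased, and the coverage in step 6 shows at most slight conservatism.

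**Conclusion.** The point stands as a conditional loss of precision. The factor balanced by the allocation is absent from the EMA primary model, without a stated reason. In the paired models the effect of leaving it out runs from a gain of about 1% in width (no residual shift) to a loss of about 11% (shift of 0.5 LogMAR), with break-even near 0.14. Mixed-model fits give larger losses under their own assumptions. The size for this trial cannot be fixed, because the residual shift, the baseline slopes and the between-eye gap are all assumed.

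The case for inclusion rests on asymmetry: a cost near 1% against a possible gain of 10% or more. It is a cheap improvement to make before unmasking. It does not call the validity of the analysis into question.

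**What to change.** Before unmasking:

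- In SAP 9.5.1, add eye status, as determined before randomisation by the algorithm in SAP 3.4, as a fixed effect in the EMA primary model.
- Replace item 8 of the EMA sensitivity analyses with the model without status.
- Align protocol 12.4.1, which describes the primary model without status, so that the two documents agree.
- State whether the analyses that reuse this model (the FDA secondary analysis and the Week 72 and Week 96 estimates) follow the change.
- If the sponsor prefers to keep the present model, give the reason in the SAP.

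The adjusted model is already planned as item 8, so the work is SAP and protocol wording. The statistical cost is one degree of freedom, and an interval about 1% wider if status adds nothing beyond baseline LogMAR.
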